In addition to targeting a vulnerable population at high risk of tobacco-related health disparities, the originality of this project stems from utilizing smartphone app, a novel, low-cost and highly scalable delivery method, to deliver mindfulness training merges a new treatment for smoking cessation in cancer patients and survivors. Mobile MT can potentially improve efficacy by bringing MT into real-world contexts, allow an intervention to be delivered in multiple methods (e.g., video, audio), and help tracking progress consistently.²³ MT helps smokers in reducing depression and gaining greater sense of control over craving by being less emotionally reactive and less prone to relapse-related distress,²³ two major predictors of smoking relapse.^{37,39,41} In addition, the RCT design will allow a direct comparison between the feasibility, acceptability, and potential efficacy for two delivery modalities for MT (group vs. smartphone app), compare to usual care.

4) Inclusion and Exclusion Criteria*

A. Inclusion Criteria

To be eligible participants should:

- Be 18 years and older
- Cancer survivors (based on the NCI definition — “a person is considered to be a survivor from the time of diagnosis until the end of life” National Cancer Institute Dictionary of Cancer Terms, 2014)⁵²
- Cancer patients currently in active treatment
- Have smoked ≥ 5 cigarettes/day in the past year
- Be interested in making a quit attempt in the next 30 days
- Own a smartphone (apple/android)
- Read/speak English
- Able to consent
- Have no plans to move in the next 3 months
- Are not pregnant or planning to be pregnant in the following 3 months

Any histologic subtype of cancer is qualified for entry into this study.

B. Exclusion Criteria

Participants would be excluded if they:

Date: 4/1/2024

Protocol Version: 5

[figure not shown]
IRB Study Number: 20190328

NCT04038255

- Have contraindication to NRT (past month myocardial infarction, history of serious arrhythmias/or unstable angina pectoris, dermatological disorder)
- Are currently being treated for a psychiatric condition.
- Are currently being treated for smoking cessation, alcoholism, or illicit drug use
- Are adults unable to consent
- Are individuals who are not yet adults
- Are pregnant women
- Are prisoners

5) Procedures Involved*

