We propose a three-arm pilot RCT among cancer patients and survivors smokers (n=30 total; 10/arm) designed to evaluate the feasibility, acceptability, and potential efficacy of: (1) the *Craving-to-Quit* vs. (2) group MT for smoking cessation, and (3) Usual Care (UC) intervention (control group). Participants in the three study arms will receive 6 weeks supplies of Nicotine Replacement Treatment (NRT). In addition to matching NRT between groups, this design allows us to compare the effectiveness of MT smoking cessation intervention delivered by *Craving-to-Quit* app vs. group MT; and whether each of the MT interventions improve cessation over the UC. Participants are randomly assigned to blocks of 6, based on gender stratification to one of the treatment arms in a 1:1:1 ratio using a computer-based random number generating. Given the pilot nature of the study, participants will be randomized in sequence for the app, the in-person, and then the UC group with the goal to reach 10 participants in each group. All participants will receive a follow-up assessment at the end of treatment and 3-months after quit date. [name], who has years of experience in training and supervising cessation trials,^{45,47,48,51} will direct and oversee the trial and will be responsible for the training of two Research Assistants (RAs) in recruitment and conduct of the cessation trial (e.g., human subjects protection, cessation pharmacotherapy, the study's protocol). The team will meet weekly with [name] for supervision, and case review. Participants will receive a \$50 incentive (\$15 at the baseline assessment, \$15 after their quit date, and \$20 at the 3-month follow up). All study procedures will be conducted remotely via Zoom. We will use REDCap to collect our data. No data are collected from the medical record.

All participants will attend an orientation session, which will be conducted via Zoom. Informational materials will be sent to participants via email or mail, and NRT will mailed.

Interventions

1. Usual Care (UC)/control: Participants in this group will receive a brief advice to quit smoking, 6-week supplies of NRT, and self-help materials to quit smoking.

Date: 4/1/2024

Protocol Version: 5

IRB Study Number: 20190328

NCT04038255

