2. Craving-to-Quit app for smoking cessation intervention: This intervention is based on the theory of mindfulness-based cognitive therapy (MBCT) for relapse prevention. The MBCT uses cognitive behavioral therapy methods in collaboration with MT techniques. Cognitive methods focuses on the development of personal coping strategies that target solving problems and changing unhelpful patterns in cognitions (e.g. thoughts, beliefs), behaviors, and emotional regulation. MT focus on becoming aware of all incoming thoughts and feelings and accepting them, but not attaching or reacting to them. This process is known as "Decentering" and aids in disengaging from self-criticism and rumination that can arise when reacting to negative thinking patterns. Participants in this group will receive one orientation session, 6-week supplies of NRT, the "Craving-to-Quit" app, and two brief follow-up phone calls.

a. *Orientation session:* This session will occur 21 days before quit date. It will be moderated by a certified instructor in MT, and will last approximately 90 min. During the session, a research associate will explain the purpose, format, and procedures of the study, and will go through the written informed consent and have the participant complete the baseline assessment. Participants will then watch a video that explains the specifics of their respective arm's study activities.

Then, participants will be instructed to download on their phone the "Craving-to-Quit" app and will receive a 60-minute tutorial explaining the app content and features to troubleshoot any issues, followed by training on how to use the app and to practice MT techniques introduced in the app. Participants will be instructed to start using the app in the next day, and set a quit date within the next 2 weeks. Participants will receive 6 weeks of NRT, and will be instructed to start using the NRT at the quit date.

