IRB Study Number: 20190328

NCT04038255

- The follow up assessment will occur at 3 months (+30 days) after quit date. The visit will last approximately 45 minutes.
- All baseline assessment will be re-administered except demographics.
- *Usability*: In the app group, measures of usability will be measured by: 1) The absolute number of times logged into the apps will be calculated for each user to obtain the mean number of using each app, 2) self-reported number of completed days for the app. And 3) level of comfort with the app “I am comfortable using the app.” In the group MT arm, we will collect information on number of sessions that was attended.
- *Acceptability*: The acceptability will be assessed by 3 items “How satisfied were you with the intervention?”, “How likely are you to recommend this intervention to a friend?” and “How useful was the intervention?” Participants in Arms 2 will also complete The System Usability Scale (SUS) at call 1 & 2 and the 3-month follow-up to evaluate the overall usability of and satisfaction with the app (John Brooke, 1986).

Feasibility: We will monitor rates of recruitment and effort required (e.g. number of staff hours) as well as the number of screenings conducted, proportion eligible, and proportion who agree to enroll. Feasibility of recruitment will be operationalized as an enrollment rate of 70% or higher (an established standard in the RCT literature). We will also record number of rescheduled, cancelled, and missed assessment visits as well as received visits/calls in each treatment arm to inform estimation of staffing needs and retention protocols for a planned efficacy RCT. Other outcomes are rate of attrition (not having a final visit at the end of treatment), rates of several categories of attrition (mortality, withdrawal from the study, transfer to non-study clinics, loss to follow-up without identifiable cause), and response rates to questionnaires (operationalized as 70% or higher), adherence/compliance rates (operationalized as completing at least 70% of the app’s module in arm 2 & 3), and time needed to collect and analyze data. As an evaluation of the feasibility of the app-based intervention, we will call participants in Arms 2 & 3 weekly during the 3-month trial to ask a brief set of questions about their mindfulness practice and use and opinions of the app.

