- *Smoking Cessation*: Main smoking cessation outcome is 7-day point-prevalence abstinence (defined as self-report of not smoking in the past 7-days; not even a puff) confirmed by expired carbon monoxide (CO) level of < 10 ng/ml at the 3-month follow up. Secondary outcome is the reduction in number of cigarettes smoked per day.^{71,72} Relapse is defined as smoking at least once/week on two consecutive weeks.⁷³
- At the end of the intervention and 3-months after the intervention, all 3 groups will be asked to complete a survey with similar items to the baseline survey.
- Breath CO will be collected at the 3-month follow-up points for participants who report abstinence. The breath sample will be collected with a

Date: 4/1/2024

Protocol Version: 5

IRB Study Number: 20190328

NCT04038255

portable CO monitor (Micro CO™ by Micro Direct, Inc.). Cut-off of <6 ppm for CO will be used to determine abstinence (Benowitz et al 2002). These portable CO monitors will be mailed to participants for data collection.

B. Aim (2). Conduct a Post-intervention Evaluation

A semi-structured post-intervention evaluation interviews will be conducted with randomly selected participants from the *Craving-to-Quit* app and group MT groups (n=30; 10/group) to further inform our assessment of acceptability and perceived helpfulness of interventions, and identifying key areas for refining the intervention protocols (e.g., improving access, content, usability).

This interview will be scheduled during or after the 3-month follow-up over the phone. It will take approximately 30-45 minutes to complete. Participants will receive \$25 for participating.

6) Data and Specimen Banking*

There will be no banking or storage of data or specimens.

7) Data Management*

The primary focus of the proposed formative clinical research will be to examine the feasibility and acceptability of *Craving-to-Quit* app and group MT for smoking cessation to inform a larger planned Phase II efficacy RCT to be considered as a R01 grant application. Although we will conduct intent-to-treat analyses of our combined intervention on primary and secondary outcomes using data from the proposed pilot RCT, this is only to explore the potential for a treatment effect. There is increasing recognition that the effect size estimates from pilot RCTs should be interpreted with caution because they lack sufficient precision for establishing efficacy or informing subsequent power analyses.⁷⁴

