Our target sample size is 30 cancer patients and survivors who smoke. The main source of recruitment will be UHealth’s Consent to Contact database. The Consent to Contact Initiative will provide a list of identified potential eligible participants who have consented to being contacted for research studies. Flyers will also be distributed at UM/SCCC clinics and various community-based clinics/organizations not directly affiliated with UM/SCCC, such as Jackson Health System (JHS). We will also recruit via advertisements on social media platforms.

We will be provided with a list of potential participants by the Consent to Contact Initiative. We will reach out to cancer patients and survivors who seem to meet criteria and have consented to be contacted for studies. We will be provided with a list of potential participants including their names, contact information, smoking status, and cancer history. Participants from the Consent to Contact list will be contacted by phone and invited to participate in the study. However, interested participants from JHS will contact our research staff first and then receive additional study information. Additionally, they may also scan the QR code included on the study flyer to complete the screening questions independently via REDCap. The staff will describe the study and screen potential participants to determine eligibility. Those who are not eligible, or decline to participate will still be encouraged to quit smoking and given a list of available resources.

Those who are eligible and want to participate will be sent them an email with a link to complete connect to Zoom with the Research Associate and complete a REDCap eConsent informed consent and then the baseline survey. During the initial phone call they will be scheduled for an orientation session and Arm 3 group sessions, if applicable.

ResearchMatch.org will be utilized as a recruitment tool for this protocol. ResearchMatch.org is a national electronic, web-based recruitment tool that was created through the Clinical & Translational Science Awards Consortium in 2009 and is maintained at Vanderbilt University as an IRB-approved data repository (**Vanderbilt University IRB #090207**).

Date: 4/1/2024

Protocol Version: 5

IRB Study Number: 20190328

NCT04038255

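### The Design section gives two allocation rules that cannot both govern, one of them deterministic if followed literally, and the recruitment text implies that the arm may be known before consent and baseline.

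*Combined protocol and SAP*

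**What the plan says.** Section 5, Aim (1), Design contains two consecutive statements on allocation.

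- The first: "Participants are randomly assigned to blocks of 6, based on gender stratification to one of the treatment arms in a 1:1:1 ratio", with a computer random number generator.
- The second, introduced by reference to the pilot nature of the study: "participants will be randomized in sequence for the app, the in-person, and then the UC group", aiming for 10 in each group.

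Two other places bear on when the arm becomes known.

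- The recruitment text before section 15 sends willing, eligible people a Zoom link to "complete a REDCap eConsent informed consent and then the baseline survey". It then adds: "During the initial phone call they will be scheduled for an orientation session and Arm 3 group sessions, if applicable". Arm 3 here must be group mindfulness training, which is third in the Interventions list and the only arm with group sessions.
- Interventions, item 2a (Orientation session) places consent and baseline inside the orientation session, and continues: "Participants will then watch a video that explains the specifics of their respective arm's study activities".

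On use of the data, section 3E says "the RCT design will allow a direct comparison between the feasibility, acceptability, and potential efficacy" of the two delivery modes against usual care. Section 7 plans chi-square tests of cessation across the three arms and between-group comparisons of adherence, retention and treatment perceptions. It says of the effect analyses that "this is only to explore the potential for a treatment effect".

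**The concern.** A random order within gender-stratified blocks and a fixed order of arms are different schemes, and the protocol does not say which governs. If the fixed order is followed, whoever enrols participants knows the next arm and can choose whom to approach, or when. If the arm is disclosed at the first call, candidates can also accept or decline by arm. Either route breaks the comparability that the randomised design is meant to supply.

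This is not confined to the exploratory cessation tests. Adherence, retention and acceptability by arm are main outputs of the pilot, and they are sensitive to who agrees to which arm. The recruitment criterion is affected as well: "Feasibility of recruitment will be operationalized as an enrollment rate of 70% or higher". If people know their arm before consenting and acceptance differs by arm, that rate partly measures which arm was on offer. Filling the arms in order would also remove concurrent control.

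**Working it through.** **Inputs.** N = 30, 10 per arm (Design); blocks of 6, 1:1:1, stratified by gender (Design); equal gender distribution, hence 15 per stratum (section 7); recruitment of 10 to 12 per month over 5 months (Study Timeline). The plan's own total reproduces: 3 × 10 = 30.

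**Can both rules hold?** A block of 6 with two places per arm has 6!/(2!·2!·2!) = 90 equally likely orders. App, group, usual care repeated twice is one of them (1/90 = 1.1%). Filling one arm to 10 first is impossible, because a block holds at most two of any arm. The text allows three readings:

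- (a) arms filled one after another;
- (b) fixed rotation;
- (c) loose drafting, with the random list governing.

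**Predictability.** Under (a) and (b), 30 of 30 assignments are known in advance. Under (c), take the worst case of staff who know the block size, the stratum and all past assignments.

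- Certain assignments per full block: the sixth always, the fifth when the last two places are the same arm (probability 1/5), so 1 + 0.2 = 1.2 of 6. None of the first three is ever certain. A stratum of 15 is two full blocks plus the first three places of a third: 2 × 1.2 = 2.4. Two strata: 4.8 of 30 = 16%.
- Best-guess hits by position: 1/3, 0.4, 0.5, 0.533, 0.6, 1, which sum to 3.367 per block (56%). The first three positions sum to 1.233. Per stratum 2 × 3.367 + 1.233 = 7.967; two strata 15.9 of 30 = 53%, against 33% by chance. With a concealed list and unknown block size the figure is close to chance.

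**Calendar time between app and usual care.**

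| Reading | Mean place, app | Mean place, usual care | Gap | At 12/month | At 10/month | At 6/month |
|---|---|---|---|---|---|---|
| (a) fill in order | 5.5 | 25.5 | 20 | 1.7 months | 2.0 | 3.3 |
| (b) rotation | 14.5 | 16.5 | 2 | 0.17 | 0.20 | 0.33 |

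The 6 per month column is 30/5. It is shown because the stated rate over the stated 5 months gives 50 to 60 people, not 30. Calendar time is material only under (a).

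**Arm sizes under the list.** 15 is not a multiple of 6. Each stratum's half block is 1/1/1 with probability 8/20 = 0.4, and each of the six 2/1/0 patterns has probability 0.1. So P(10/10/10) = 0.4² + 6 × 0.1² = 0.22. A 9/10/11 split has probability 0.60, so all arms lie within 9 to 11 with probability 0.82. The full range is 8 to 12. This is a minor point.

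**Timing of disclosure.** The recruitment text puts the booking of group sessions at the initial call, and eConsent and baseline at a later Zoom contact. The orientation text puts consent and baseline inside a session that the call only schedules. On either account they follow the call. Unless the booking is provisional, whether group sessions apply can be settled at the call only if the arm is known by then.

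**The case against.** The disputed sentence still uses the word randomized, follows directly on a computer-generated scheme, and ends with a target per arm. The study is called a randomised trial throughout. It may simply be a clumsy account of how slots are filled, in which case allocation is sound. That reading is possible, but the sentence is offered as a concession to the pilot setting, which reads more like a departure than a paraphrase. Staff still could not tell which rule to follow.

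The point about disclosure is an inference. The recruitment text is loosely ordered, sessions could be booked provisionally, and the arm-specific video after consent and baseline fits later disclosure. No text available for this review states when randomisation occurs, and parts of the protocol were not available, so nothing is concluded from that silence. The effect on the 70% criterion needs both early disclosure and acceptance that differs by arm, and the protocol gives no figure for either. These limits stand.

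The stakes are also reduced, because efficacy is exploratory and the feasibility analysis mainly descriptive. That lowers the impact but does not remove it, since the planned between-arm comparisons of adherence, retention and perceptions rely on the same allocation. Nor does any figure in the protocol show that a gap of two or three months would shift outcomes.

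**Conclusion.** The concern holds. The two allocation statements cannot both govern. Followed literally, the second makes all 30 assignments predictable, against about 16% certain under the block list in its worst case. If the arms are filled in order, app and usual care are separated by 1.7 to 2.0 months at the stated recruitment rate, or 3.3 months if 30 people are spread over 5 months. These figures assume 15 per gender and steady accrual. If the random list in fact governs, allocation is adequate and the defect is one of wording.

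That the arm is known before consent and baseline is implied by the recruitment text, not established. The contradiction must be resolved before the comparisons between arms can be described as randomised.

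**What to change.** State which rule applies, and replace the in-sequence sentence with a single rule:

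- a concealed, computer-generated list in permuted blocks, stratified by gender;
- a stated time of randomisation, with each assignment released only after eConsent and the baseline survey;
- group sessions booked after release, with the recruitment text and the orientation text brought into line;
- replacements for withdrawals (section 7) taking the next slot on the same list;
- 10 per arm described as approximate.

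If exact balance matters more, blocks of 3 give 10/10/10 at 15 per gender. The third place in every block is then certain to anyone who knows the block size (10 of 30). That trade-off is for the team.

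If groups have to be assembled, consented participants can be randomised in batches across all three arms. This is optional.

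**Cost.** If the list is what is used, only wording and the order of steps change, with a short wait for group participants while sessions are booked. Batching would delay all three arms after baseline, and it has to be squared with the eligibility requirement of interest in a quit attempt within 30 days and with the quit-date timing in the orientation text. If anyone has already been allocated in sequence, they cannot be re-randomised. The report must say so and must not describe their allocation as random.

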b. *The Craving-to-Quit app:* The app is comprised of 22 modules for 22 days, 5–15 minutes each, designed to teach MT using audio, video, and animation. Participants have access to only one new module per day, and subsequent days are locked to prevent skipping ahead (pls. see LOS from [name] from MindSciences). The app teaches three basic formal MT techniques including Body Scan (bringing awareness to different parts of the body to foster awareness of body sensations that constitute cravings and affective states), Loving-Kindness (repeating phrases such as "may X be happy" to foster acceptance of oneself and others), Breath Awareness (paying attention to the breath wherever one feels it most strongly in the body to help retrain the mind away from habitually engaging in self-related thinking toward a more present-centered awareness), and one informal MT RAIN (Recognize, Accept, Investigate, and Note what cravings feel like as they arise/pass away). In RAIN, participants are asked to identify their smoking trigger, rate their craving, and choose between using RAIN to ride out their craving, or completing an audio-guided exercise to 'smoke mindfully' by paying attention to the moment-to-moment experience and bodily sensations of smoking. The app also includes other features such as social support (quit friend sign-ups, the tip of the week), activity feed (to track interaction with the app), and my morning stats (to track smoking).

Date: 4/1/2024

Protocol Version: 5

IRB Study Number: 20190328

NCT04038255

c. *Two brief follow-up phone calls.* The first phone call will occur one day before the quit date to remind participants about their quit date and provide support. The second will occur at the end of treatment (around day 60 after quit date) to review progress, provide support, and schedule the 3-month follow-up visit. Each phone call will last approximately 15 minutes.

3. The group MT smoking cessation intervention:

Participants in this group will receive twice weekly group sessions (eight total during 4 weeks) that were manualized and delivered by instructors experienced in MT (a single therapist with >4 years of training in MT). The intervention includes components that are well-matched with Craving-to-Quit. The overarching theme of momentary awareness and acceptance of cravings and affect (e.g., stress, anxiety etc.) will be introduced and reinforced in complementary ways throughout the training. Each session will last 45-60 minutes.

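### The only adherence threshold counts app modules in arms 2 and 3, but only one arm is described as having the app, so the rule fails under either arm order in the protocol

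*Combined protocol and SAP*

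**What the plan says.** In section 5, under Three-month Follow-up Assessment, Feasibility, adherence or compliance is "operationalized as completing at least 70% of the app’s module in arm 2 & 3". No other adherence threshold appears in the text available for review.

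The Interventions list in the same section numbers the arms:
- "1. Usual Care (UC)/control: Participants in this group will receive a brief advice to quit smoking"
- "2. Craving-to-Quit app for smoking cessation intervention"
- "3. The group MT smoking cessation intervention"

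Two other places use arm numbers that agree with this list. The Acceptability item says "Participants in Arms 2 will also complete The System Usability Scale (SUS"), which is the app usability scale. The recruitment text says eligible people will be "scheduled for an orientation session and Arm 3 group sessions, if applicable".

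On content, "The app is comprised of 22 modules for 22 days", whereas group MT consists of "twice weekly group sessions (eight total during 4 weeks"), with suggested home practice and a meditation CD. The Usability item records how many sessions each group MT participant attended, without a threshold. Section 7 (Data Management) plans chi-square tests and one-way ANOVA for between-group differences that include adherence.

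**The concern.** Section 7 makes feasibility and acceptability the main purpose of the pilot, to inform a larger efficacy trial. Adherence is one of the few feasibility outcomes with a numeric criterion, and that criterion is expressed in a unit that one of the two active arms does not appear to receive. An analyst who follows the text must either score every group MT participant as non-adherent or leave that arm blank. Neither result says anything about attendance at group sessions, and the first would make the app look better than the group purely because of how the outcome is worded.

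**Working it through.** The plan has no calculated figure to reproduce here. The check is one of consistency, followed by short arithmetic.

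**1. Which arm is which.** The protocol uses two orders.

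| Source | Arm 1 | Arm 2 | Arm 3 | Of arms 2 and 3, which has the app? |
|---|---|---|---|---|
| Section 5, Interventions list | Usual care | App | Group MT | Arm 2 only |
| Section 5, opening text and Design paragraph | App | Group MT | Usual care | Neither |

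The usability scale and the recruitment text fit the first row. Since only one arm is described as having the app, no numbering can make a module rule work in two arms.

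**2. A second instance.** The Feasibility paragraph ends by having staff telephone arms 2 and 3 every week with questions that include how participants use and regard the app. This is the same mismatch, and correcting only the adherence rule would leave it in place.

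**3. What the literal rule produces.** Inputs: 10 per arm (Design paragraph), 22 modules in the app arm, none in group MT.
- Participants for whom the rule has no meaning: 10 of 10 + 10 = 20 active-arm participants, or 50%.
- Highest possible pooled adherence over the two arms if group MT is scored as zero: (10 + 0)/20 = 50%, below the protocol's own 70% even if every app participant complies.
- Illustration, assuming 5 of 10 app participants are adherent against the built-in 0 of 10: chi-square = 20 × (5 × 10 − 5 × 0)² / (10 × 10 × 5 × 15) = 50,000/7,500 = 6.67, p = 0.0098 without continuity correction (0.039 with it). Fisher's exact p = 2 × C(10,5)/C(20,5) = 2 × 252/15,504 = 0.033. The difference comes from the definition alone.

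**4. What 70% means in each arm's own unit.**
- App: 0.70 × 22 = 15.4, so at least 16 modules (16/22 = 72.7%; 15/22 = 68.2% falls short).
- Group MT: 0.70 × 8 = 5.6, so at least 6 sessions (6/8 = 75.0%; 5/8 = 62.5% falls short).

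**5. Precision of either rate.** For 7 of 10 adherent, the exact (Clopper-Pearson) 95% limits are the 2.5% point of Beta(7, 4) and the 97.5% point of Beta(8, 3): 34.8% to 93.3%.

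**The case against.** The best defence is that the intent is recoverable. Session attendance is already collected, section 7 calls the feasibility analysis mainly descriptive, and the comparison of adherence is not tied to the yes/no version. A count of sessions could be reported with no threshold. This stands in part: a reader might infer that adherence in group MT cannot be measured at all, and the documents do not support that. What fails is the rule as worded.

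A reader might also infer that the group threshold would have to be picked after attendance is known. The documents do not show that. The protocol uses 70% for enrolment, questionnaire response and adherence alike, and 6 is the smallest session count that meets it, so the threshold is nearly determined and can be set in advance.

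Finally, the Feasibility paragraph pairs arm 3 with the app twice, which could mean that group participants are given the app too. The description of group MT mentions none, and the Design paragraph contrasts app delivery with group delivery, so no app is the better reading. It remains an inference for the sponsor to confirm.

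**Conclusion.** The adherence rule is wrong as written, not merely short of detail. Under the Interventions numbering it cannot be applied to group MT; under the design-text order it applies to no arm that has the app. It leaves 10 of the 20 active-arm participants with a built-in zero or no value on a stated feasibility outcome. This rests on 10 participants per arm and on group MT having no app. The 5-of-10 comparison is illustrative, not a forecast.

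The reach is limited to one mainly descriptive outcome. The sample size and the cessation outcome do not depend on it, and the available text ties no progression decision to it.

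A minor clarification belongs alongside. Adherence to ART is a three-month assessment item (section 5, Retention) and a regression outcome (section 7), but ART is not defined in the text available and matches no trial treatment. A reader might take it as a slip for NRT; the documents do not settle this, and the Retention text names NRT separately in the same sentence. It affects only an exploratory model.

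**What to change.** 1. Confirm that group MT participants receive no app. Then limit the module rule to the app arm, at least 16 of 22 modules, and define adherence in group MT as at least 6 of 8 sessions, using the attendance already collected. Fix both before the adherence data are analysed.
2. Name the source for the module count. Log-in counts do not measure modules; self-reported completed days can, because one new module opens per day.
3. Report the two rates separately by arm with exact 95% intervals, as parallel but not equivalent measures. State that usual care has no such measure and is outside this comparison.
4. Use one arm numbering throughout, reconciling the opening and Design text of section 5 with the Interventions list, the follow-up assessment and the recruitment text. Correct the weekly-call sentence at the same time.
5. State what ART means, and define that outcome, before running the regression.

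Items 1 to 4 change wording and use data already planned. Item 5 is also wording only if the follow-up questions capture the treatment meant. Two limitations remain: a module and a session are different amounts of treatment, and app adherence may rest on self-report.
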